**If there are no questions, move on to the next section**

### **Describe Surveys:**

Four times during the 12-week study you will be asked to complete some questionnaires online.

- The first time will be today after we finish with our call. I will be sending you the links to our online consent form and also the link to the first set of surveys for you to do.
- As a kind of addendum to today's surveys, I'll also be sending you a link to a really quick survey for you to do after your next session.

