Think of the positive consequences of tolerating the distress. Imagine in your mind how good you will feel if you achieve your goals, if you don't act impulsively.

Think of all of the negative consequences of not tolerating your current distress. Remember what has happened in the past when you have acted impulsively to escape the moment.

Ask yourself, "*Will this event that is distressing me going to matter in 5 years?*"

WILLOW RCT
Mood Assessment and Debrief Protocol

**Adapted from Linehan's
Suicide Risk/Distress Assessment Protocol**

PURPOSE:

While the risk is deemed low, the intent of this Mood Induction Protocol is to ensure that research patients are not at imminent risk to harm or kill self following completion of a study assessment.

PROCEDURE:

Before concluding each assessment, the patient will complete the Mood Assessment online. If the patient reports a score of 5 or greater on items 3a, 3b, 4b, they will receive a message from the survey system. This message will include validation of their experience and suggestions for improving their mood through the use of behavioral skills. Specific changes are detailed below.

MOOD ASSESSMENT:

1. Feedback on their experience during this assessment and other experiences they have had with the study (i.e., other assessments -- how did this one compare? How was it different? What made the difference?). Describe.

2. ____ On a scale of 0 to 7, what is your level of stress right now?

Low 0 1 2 3 4 5 6 7 High

- 3a. ____ On a scale of 1 to 7, what is your urge to harm yourself now?

Low 0 1 2 3 4 5 6 7 High

- 3b. ____ On a scale of 1 to 7, what is your intent to kill yourself right now?

Low 0 1 2 3 4 5 6 7 High

4. ____ On a scale of 1 to 7, what is your urge to use drugs or alcohol right now?

Low 0 1 2 3 4 5 6 7 High

- 4a. ____ On a scale of 1 to 7, how angry are you (i.e., what is your level of anger right now)?

Low 0 1 2 3 4 5 6 7 High

- 4b. ____ On a scale of 1 to 7, what is your intent to physically hurt another person right now?

Low 0 1 2 3 4 5 6 7 High

If the patient endorses a score of 5 or greater on items 3a, 3b, 4b, they receive the following message:

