Thank you again for completing these surveys today. I look forward to hearing back from you.

Kind Regards,

xxx

STEP 1: ORIENT TO MOOD INDUCTION / ELICIT PERMISSION

You mentioned on a mood rating that you are feeling <<insert what person endorsed, "like harming yourself" or "like killing yourself" or "like harming someone else">>. I just want to make sure that you're in good shape before we hang up. Would it be okay with you if we take a few moments to see if we can get your mood up a bit before we hang up?

STEP 2: DUE TO ASSESSMENT?

Is how you're feeling now like how you often feel, or does it feel worse than typical, maybe because of going through the study processes?

Unusual	Go to Step 3: VALIDATE
Typical	Go to Step 4: ASSESS/OFFER SKILLS

STEP 3: VALIDATE IF DUE TO ASSESSMENTS

It's not uncommon for people who are completing an assessment like this one to notice a drop in their mood.

STEP 4: HAVE COPING STRATEGY THEY CAN USE NOW?

Assess Skills. *Are there things that you have found helpful to do in situations like this? (Pause for participant's response. If needed, then): Perhaps you and your therapist have identified something that is helpful for you to try in situations like this to improve your mood...*

If No Skills Named: Go to Step 5.

If Skills Named, Encourage Their Use: *Would you mind sharing with me what you find helpful to do in situations like these? (Listen to strategies. Are they functional behaviors that you could image doing yourself or recommending to a loved one to try? If yes, then encourage their use. Before moving off this step and moving to Step 6, make sure the plan they identify can actually be implemented. If solution proposed is dysfunctional or potentially harmful e.g., I'm going to smoke a bowl of pot, then consider saying): Would it work for you if I also offered up an additional skill that you may find helpful? (Then proceed to Step 5).*

STEP 5: PROVIDE HELP

Ask Permission: *Would it be okay with you if I offered some suggestions that may help improve your mood?*

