Inquire About Something Non-Stressful: *How about if we start by you telling me something about your life that is pleasant or positive. (Pause for participant's response. If participant pauses a while or indicates that nothing comes to mind, then ask follow up): It may be that there's nothing particularly pleasant or enjoyable happening in your life right now. How about instead telling me something that's ordinary and not stressful in your life right now. [Listen with interest; ask simple, casual questions about what participant has said that draws him/her out a bit more, just as you might at a public social event. In other words, if you would not ask your question to an acquaintance in a public setting, if is probably NOT a good follow up question].*

Reassess Mood: *How are you feeling now? (Pause for participant's response. If clarification is needed, then ask following): Do you feel that your mood has improved from where it was? [If mood has improved, go to Step 6. If it has not, continue on].*

Teach Additional Coping Skills: *Could I offer you some coping strategies? These are behavioral skills that you may find useful to also help improve your mood. I'd like to teach you a couple that may be helpful to you. Is that okay? (Pause for participant's response then proceed): There is a set of skills called TIPP that I'd like to introduce you to. Each letter stands for a different skill. I'll tell you what they are and then we can figure out which one or two you'd like to try. The T stands for Temperature... (Orient participant to TIPP skills individually at a high level. Make sure to mention that if participant has any heart problems or concerns, skip the T and move to the others. Once reviewed ask the following question): Which of these skills would you like to try first? (Pause for participant's response. Proceed with teaching and practicing the skill selected, then ask): How are you feeling now? Would you like to learn and practice another? (Assess participant's mood and interest in learning another. It may be the case that participant's mood has improved AND they still*

wish to learn a new skill. If this is the case, teach them another skill. If participant is not feeling better, skip to Step 8).

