If Participant Is Reluctant to Engage in Problem Solving Efforts to Change Mood: (Ask participant): *Is there something else that might be going on for you right now that might be helpful to talk about for a few minutes?* (If there is, just thoughtfully listen for a few moments. When the conversation winds down naturally, state): *I am really glad we talked about that. How are you feeling now?* (Listen with ear to determining whether it would be helpful to teach a skill or two. If it would be helpful, ask participant if he/she would like to learn some skills that may be helpful to them): *I definitely don't want to push to figure out a plan with me (or to learn skills). I do just want to make sure you're okay before we hang up. Would it be helpful to try out a skill?* (If they do not wish to, move to **Identify Who they Can Call if Needed**.

STEP 6: COPING AHEAD AFTER HANGING UP

Identify a Plan. *Before we get off the phone, I want to make sure you're set and in good shape. Would that be okay?* (Pause for participant to respond. If participant wants to terminate call before completing this step, skip to Step xx. Otherwise proceed): *What ideas do you have for what you might if you start feeling distressed again?* (Elicit one or two ideas from participant [If no ideas, identify one or two things person can do to distract themselves. Use Crisis Survival Handouts for WiseMind ACCEPTS and Self-Soothe if need to generate ideas].

Identify Who they Can Call if Needed. *Would it be helpful for us to figure out whom you might call if you need a bit more support later? Do you have someone you usually call when you're feeling down?* (Pause for participant's response. Help generate ideas of who the best person might be to reach out to in their social support network. If there is no one or if participant is hesitant to contact someone in network, then proceed with following): *What about your therapist? Is that someone you might reach out to?* (Pause for participant's response. If unable/unwilling to call therapist but a contact is needed, proceed with): *May I then give you the phone number for the national crisis hotline?* (Before proceeding, make sure participant has phone number for person/organization they agree to call): *Do you have <<insert name's>> phone number if you need it?*

STEP 7: CONCLUDING THE CALL

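### The printed debrief script never re-asks the self-harm, suicide or violence item that triggered the call, and its early exit points to a step that does not exist

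*Protocol*

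**What the plan says.** The Mood Assessment and Debrief Protocol states its aim under Purpose: "the intent of this Mood Induction Protocol is to ensure that research patients are not at imminent risk to harm or kill self" after a study assessment. Under Procedure, "Before concluding each assessment, the patient will complete the Mood Assessment online". A score of 5 or more on 3a, 3b or 4b brings an automatic on-screen message, and a research assistant then calls and works through Steps 1 to 8.

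The steps that decide how the call proceeds are these:

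- **Step 2** asks whether the feeling is usual for the patient, "or does it feel worse than typical, maybe because of going through the study processes".
- **Step 4**, for a patient who names a functional strategy: "Before moving off this step and moving to Step 6, make sure the plan they identify can actually be implemented".
- **Step 5**, after a neutral conversation: "If mood has improved, go to Step 6. If it has not, continue on". After skills teaching, a patient who feels no better is directed to Step 8.
- **Step 5**, for a reluctant patient who is offered a skill: "If they do not wish to, move to" the part of Step 6 that identifies someone to call.
- **Step 6**, early exit: "If participant wants to terminate call before completing this step, skip to Step xx".
- **Step 7** summarises the plan, seeks agreement to it, invites remaining questions and says goodbye.
- **Step 8** is the crisis step. Apart from the directed route from Step 5, entry is at the research assistant's judgement. The supervisor is called if the patient appears unresponsive or will not accept help.

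**The concern.** The call opens on three specific items and closes on something else: a workable plan, general mood, or a declined offer of help. The Mood Assessment scores stress, anger, substance urge, self-harm urge, suicidal intent and intent to hurt others separately, and only three of these trigger a call. Better general mood is therefore not the same finding as a triggering item that has fallen below 5.

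At stake is a calm, cooperative patient whose suicidal intent persists. That patient can name a good strategy, agree to a plan and be released without anyone learning whether the intent is still at 5 or more. Nothing in such a call need meet the condition for calling the supervisor. The informed consent call tells patients that their research answers do not go to the treatment team, so this call may be the main check on that day.

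The undefined exit falls where a patient who has just reported high risk wants to leave the call, and the research assistant has no printed instruction there.

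**Working it through.** There is no sample size, power or event figure to reproduce. The check follows each printed route through Steps 1 to 8 and asks two things: is 3a, 3b or 4b asked again, and does every onward reference have a target?

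**Routes**

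- *Steps 1, 2, (3), 4, 6, 7.* The gate is an implementable plan. The item is not re-asked, and Step 5's general mood question is bypassed.
- *Steps 1, 2, (3), 4, 5, mood improved, 6, 7.* The gate is general mood. The item is not re-asked.
- *Steps 1, 2, (3), 4, 5, skills taught and feeling better, then on to 6 and 7 in sequence.* The gate is general mood. The item is not re-asked.
- *Steps 1, 2, (3), 4, 5, reluctant, second half of 6, 7.* The gate is that a skill is declined, after a general question about feeling. The item is not re-asked.
- *Steps 1, 2, (3), 4, 5, not feeling better, 8.* Entry is directed by the script. Step 8 does not re-ask the item, makes the supervisor call conditional, and has no printed return to Step 7.
- *Early termination at Step 6.* The item is not re-asked, and the target is undefined.

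Step 1 repeats back what the patient endorsed but takes no new rating. Step 2 comes before any skill and compares with the patient's usual state, so it is not a re-rating either.

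**Target check.** The script announces Steps 1 to 8. Step xx is an unfilled cross-reference. It is not a redaction, because removed details appear as bracketed placeholders. Step 7 may be what was meant, but the text does not say so.

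**Against the purpose.** The Purpose covers risk to self, so 3a and 3b can be measured against it. Item 4b is a trigger that the Purpose does not mention. The missing re-ask applies to it too, but not as a shortfall against that sentence.

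**Burden of a re-ask**

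- Triggering items per call: 1 to 3 (3a, 3b, 4b).
- Assessments per patient: 4 (baseline and weeks 4, 8 and 12). The consent call script says "Four times during the 12-week study you will be asked to complete some questionnaires online".
- Upper bound: 3 items × 4 assessments = 12 questions per patient, reached only if every item triggers at every assessment.
- Assumption: the short satisfaction survey after the first study session carries no Mood Assessment. If it did, the bound would be 3 × 5 = 15.

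The documents give no trigger rate, so neither the number of affected calls nor the number of supervisor contacts can be estimated.

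**The case against.** The strongest objection is that the working record for this call cannot be seen. Step 9 of the Patient Protocol has the research assistant complete a SurveyMonkey debrief form while talking to the patient, and the printed flowchart text jumps from Step 2 to Step 8. Either could contain a re-rating or an alert. This stands: an absence from the script is shown, an absence from the procedure is not. A reader might infer that the study never re-checks risk, and the documents do not support that.

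A reader might also infer that escalation is left entirely to discretion, or that nobody else is told. Neither follows. Step 5 directs a patient who feels no better to Step 8. The flowchart has an instruction to inform the clinic; its scope is unclear and the full-text Step 8 lacks it, but it rules out the claim that nobody is told.

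Third, no document requires a numeric re-rating, and the script is a coherent clinical approach. It names the endorsed feeling, asks at three points in Step 5 how the patient feels, redirects a harmful strategy, identifies a support contact or hotline, and seeks agreement to the plan. The automatic message gives study numbers, a lifeline and 911. The flowchart has an acute-skills branch, and therapists screen for imminent suicide risk at intake. These are real safeguards. None re-asks the triggering item, and intake screening does not cover weeks 4, 8 and 12. The Step 4 route is the hardest to defend, because it misses even the general mood question.

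Last, Step xx may be only a drafting slip for Step 7. Even so, Step 7 assumes that a plan exists, and a patient who stops at the start of Step 6 may not have one.

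**Conclusion.** The point holds for the printed script. No step re-asks 3a, 3b or 4b; the Step 4 to 6 to 7 route requires only an implementable plan; and the early exit has no target. For 3a and 3b, the script can close a call without the check that its own purpose needs.

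This is a cheap improvement to participant safety. It changes no statistical result, and no rate of missed cases is claimed. It rests on the printed Steps 1 to 8, and on the unseen form and flowchart pages not already containing a re-rating. If they do contain one, only the Step xx correction remains. The SAP is written in the past tense, so if conduct has ended, the benefit lies in correcting the script before it is reused. Confidence is medium because of the unseen form.

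**What to change.** First check the SurveyMonkey debrief form. Unless it already does the following, amend the script:

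1. Before ending the call on every route, including Step 8 and early termination, re-ask each triggering item on the same 0 to 7 line and record the answer.
2. If any item is still 5 or more, call the listed supervisor before the call ends.
3. Replace Step xx with the re-ask, then give a support contact or the crisis hotline number as in Step 6, and close. Use the Step 7 plan summary only if a plan was made.
4. If the patient hangs up or declines to re-rate, tell the supervisor, who decides on provider contact within the permissions recorded under Step 4, Action Steps after Informed Consent Call. Provider contact does not become automatic for a patient who has been reached, so the existing voicemail and email wording stays true.

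The questions themselves cost little: one to three on a call already being made, within the bound of 12 per patient. The larger cost is a new escalation duty for the existing supervisors, who must be available whenever an item stays at 5 or more, or a patient leaves or refuses. The team should estimate that load from its own trigger counts before adopting the rule.

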- You will be randomized to one of two conditions: the WILLOW condition or standard care condition.
- If you are randomized to the WILLOW condition, you will be asked to use a computer in session to guide you through conducting Behavioral Activation for the treatment of depression.
- If you are randomized to the standard care condition, you will be asked to conduct treatment as you normally would.
- In both cases, we will ask that you meet with 2-5 research patients for 12 weeks each. You can choose to treat as many study patients as your schedule allows. Patients that

WILLOW Full RCT Therapist Protocol

are enrolled in the study with you will need to be new patients to your clinic and must not have received treatment from you previously.

- You can still use WILLOW with your patients who are not involved in the research study.
- Participants in both conditions will be asked to complete one online survey before starting the study (baseline) and another set of online surveys with a brief telephone interview after 4, 8 and 12 weeks for each research patient they treat. You will be compensated \$50 for each 4 week and 8 week survey, and \$60 for each 12 week survey you complete.
- You will be eligible to obtain free access to WILLOW for 12 months after the completion of your participation, which involves successfully recruiting at least 1 study patient and completing all assessments for that patient.

Does this sound like something you would be interested in?

If no, thank them for their time and hang up.

If yes, proceed to the next section.

Awesome! The next step would be for you to read and sign a consent form.

The entire process takes about 15-20 minutes. I will send you an email shortly that contains the link to the consent form and we ask that you complete it within the next two days. After completing the consent form, we will randomize you to either the WILLOW condition or the standard care condition and follow up with orientation brief call to explain the next steps.

Do you have any last questions for me?

Thank you so much for your interest in our research. Please don't hesitate to contact us if you have any questions as you are reviewing the consent form. Have a great day!

Step 3: Send Consent Survey

1. Send therapist consent survey email
2. Log date consent sent in the [Summative Tracking DB](#)

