- c. Record the Date Randomized, UI number, and Condition in the 'Randomization' tab in the Summative Tracking DB
- d. Email Research Assistant once participant is randomized

Step 6: Therapist Warm Phone Call & Baseline Survey

1. If they don't pick up, leave a voicemail and send appropriate email, script below.
2. Call them back every 2 days until you reach them.

Voicemail Script:

Hi this is _____ from the Depression Treatment Study. Sorry we missed you. Thanks so much for submitting your consent form and enrolling in our study! We would love to schedule a time to tell you more about the study and the next steps of your participation. We are eager to get started and I hope to schedule a time to talk with you soon. Please give us a call back at (phone #) when you have 10-15 minutes for a quick call or let us know when a good time for us to call you back would be.

3. If they call you back
 - a. And it is a good time for you to talk: Go through the script below
 - b. And it is not a good time for you to talk: Schedule a time you can call them back.
 - i. Log call time and date in the Pilot RCT Calendar
 - c. Log the call in the cover sheet
4. If they pick up, use the script below:

Warm Call & Baseline Script:

<<customize as needed for pilot therapists>>

Hi, this is _____ and I'm calling from the Depression Treatment Study. Thank you for completing our consent form and enrolling in the the study! We would like to briefly review the study procedures and let you know what the next steps are for your participation. Is this a good time to talk?

If it is, proceed.

If not, schedule a time to call back later. [Log the call in the tracking sheet, update the date of the call in both tracking sheet and database, and enter this new date into the calendar]

We are super excited that you decided to participate in this study! As a reminder, this study will compare how clients respond to different ways of delivering treatment for depression. You have been randomly assigned to the **[Standard Care or WILLOW]** condition.

WILLOW Full RCT Therapist Protocol

<<For pilot therapists enrolling again: *You will still be assigned to [Standard Care or WILLOW] condition*>>

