This means that we will ask you to treat 2-5 study patients over the next 4-6 months, depending on when your study patients are enrolled in the study, for 12 weeks each using **[your usual method of treating depression or WILLOW]**. We'll provide more information about your study condition after you complete the first set of study surveys. For now, we just wanted to make sure you will be available to participate in the study for 4-6 months and have room on your caseload for 2-5 study patients over this time. Does this sound doable?

If no, troubleshoot: is there any assistance we can provide to help you with this? What is needed for you to be able to treat study patients?

If yes, Great! We're so happy this will work for you!

The next step for your participation is to complete the first set of surveys. These are set up online and I will send you a link to access the surveys after our call today with instruction about how to log in to complete them. The email address I have on file is [email address]. Will this be the best email address to send the surveys to? We'll ask that you complete the surveys within 48 hours. Is this doable? Ideally, we would love if you were able to log in to complete the surveys after our call today. Is this possible? If not, when can we expect you will be able to complete the surveys by?

Once you complete the baseline survey, we will give you a call to tell you more about the study and review the study procedures in depth. Let's schedule a time for us to talk. I expect this call to take approximately 20-30 minutes. What day and time in the next week or so would work best for you? Remember, we need to have your first set of surveys completed by this time.
[Schedule call, record on cover sheet, in tracking DB, and add to calendar]

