Wonderful! Thanks so much for taking the time to talk with me today. I will send you an email right after we hang up that includes a copy of your signed consent form for your records and the link to the baseline assessment. Remember, we will need you to complete the surveys within the next 48 hours. If you have any questions as you are completing the surveys, please contact us immediately. We're here to help! I look forward to talking with you again on **[day, date, time that you scheduled orientation call]**!

2. Send therapist the Baseline Survey email and attach their signed consent form and HIPAA authorization
 - a. Make sure to attach their signed HIPAA and Consent form.
 - b. Check every day
 - c. Send reminder email if Baseline surveys are not completed within 48 hours, baseline must be done before orientation call
3. Record all scheduling information in Summative Tracking DB, including when orientation call is scheduled, when BL surveys were sent

Step 7: Therapist Orientation Call

1. If they don't pick up, leave a voicemail and send appropriate email, script below.
2. Call them back every 2 days until you reach them.

Voicemail Script:

Hi this is _____ from the Depression Treatment Study. Sorry we missed you. I had in my calendar that we were scheduled to speak today, Day, Date at Time. If you receive this message in the next few minutes, please give me a call back at (phone #). Otherwise, we would love to reschedule a time to review the study procedures and the next steps for your participation. We are eager to get started and I hope to talk with you soon. Please give us a call back at (phone #)

WILLOW Full RCT Therapist Protocol

when you have 15-20 minutes to talk or let us know when a good time for us to call you back would be.

3. If they call you back

- a. And it is a good time for you to talk: Go through the script below
- b. And it is not a good time for you to talk: Schedule a time you can call them back.
 - i. Log call time and date in the Pilot RCT Calendar
- c. Log the call in the cover sheet

4. If they pick up, use the script below:

Calling Script:

Hi, this is _____ and I'm calling from the Depression Treatment Study. Thank you for completing our baseline survey! We would like to tell you more about our study procedures at this time. Is this a good time to talk?

If it is, proceed.

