PracticeGround: Transforming Training and Delivery of Mental Health EBPs

NCT02314624 | Statistical Analysis Plan | February 8, 2020

Analysis Strategy

We conducted all analysis in IBM SPSS V19. We used the Generalized Linear Model to examine the between-condition change over time on study outcomes. The effects of primary interest were those reflecting the effects of WILLOW. For outcomes measured at baseline and follow-up points, that was the Time X Condition effects (measuring between-condition change from baseline). For outcomes measured only at follow-up points (e.g., therapeutic alliance and use of evidence-based therapy tasks), that was the Condition effects since they would represent average between-condition differences during the time patients received services. As previously mentioned, providers completed questionnaires for each study patient they treated. Hence, the provider sample size reflects the number of patients they answered about, not the number of providers. Several providers participated in the study concurrently with multiple patients. Patients were included in the analyses only if they attended five or more sessions with a participant provider.

Preliminary analyses provided important information guiding our strategy. First, we found no statistically significant differences between conditions on baseline measures. Second, we computed the design effects due to this nested design to determine the extent to which the intraclass correlation due to clustering and size of the cluster affected the analyses. Design effects ranged up to 1.8. Because all were under 2.0, we did not adjust analyses to account for clustering effects (Muthén & Satorra, 1995). For providers meeting participating in both studies, we used their Study 1 data for outcomes except for outcomes measured only in Study 2. For those outcomes, we used their Study 2 data.

References

Muthén, B.O. & Satorra, A. (1995). Complex sample data in structural equation modeling. *Sociological Methodology*, 25, 267-316. doi: 10.2307/271070

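### The therapist baseline survey, and the first scripted availability check, come after the therapist has been randomised and told the arm

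*Protocol*

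**What the plan says.** In the Therapist Protocol, Step 2 (consent call) tells the therapist: "After completing the consent form, we will randomize you to either the WILLOW condition or the standard care condition". Step 5 randomises in Minim Py and ends with the instruction "Email Research Assistant once participant is randomized". Step 6 is the warm call. Its script opens by naming the arm ("You have been randomly assigned to the" followed by the condition). It then states the task for that arm ("This means that we will ask you to treat 2-5 study patients over the next 4-6 months") and asks about time and caseload room: "For now, we just wanted to make sure you will be available to participate in the study for 4-6 months". Next it turns to the baseline: "The next step for your participation is to complete the first set of surveys". For WILLOW therapists, the same call goes on to describe the tailored training, the Feature Review and the $100 paid for passing it. The survey link is emailed after the call. The only ordering rule is that "baseline must be done before orientation call", and that call is Step 7.

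The SAP (Analysis Strategy) tests outcomes that have a baseline by the Time X Condition effect, described as "measuring between-condition change from baseline". It tests outcomes measured only at follow-up by the Condition effect. It reports no statistically significant baseline differences, and gives no rule for randomised therapists who leave before contributing a patient.

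**The concern.** Therapists are the randomised units. A baseline is protected by randomisation only if knowing the arm cannot have influenced it. Here the therapist answers after hearing the arm, and the two arms have by then been briefed differently. If that moves the answers, the change-from-baseline contrast subtracts something that is partly an arm effect.

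The second issue is retention. The first scripted point at which a therapist is asked to confirm 4-6 months and room for 2-5 patients comes once the arm is known. Willingness to go on could then depend on the arm: a Standard Care therapist may be disappointed, or a WILLOW therapist may be put off by the extra training. Loss at that stage falls after allocation and before any patient is enrolled, so a patient-level analysis would not show it.

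**Working it through.** The documents give no sample size, SD, drop-out figure or effect size for this point, so there is no figure to reproduce. The check is of sequence first, then of what the sequence can do.

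**1. Order of events (Therapist Protocol)**

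| Step | Event | Arm known? |
|---|---|---|
| 1 | Screening survey (items not shown) | No |
| 2 | Consent call: load of 2-5 patients for 12 weeks each is stated; therapist asked about interest | No |
| 3-4 | Consent survey sent and logged | No |
| 5 | Randomisation | Assigned |
| 6 | Arm named; availability and caseload question; WILLOW training and payment described; baseline link sent | Yes |
| 7 | Orientation call; baseline must be in | Yes |

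One line does not fit. Step 4, item 1 has staff checking for consent and baseline together. The next item, however, prepares documents to go out with a later baseline email, which agrees with Step 6.

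**2. What a disclosure shift does to the contrast**

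Let δ be the between-arm shift in mean baseline caused by knowing the arm, and p the share of it still present at follow-up. Let T be the follow-up contrast apart from this shift.

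- Change from baseline: T + pδ − δ = T − (1 − p)δ, so the bias is −(1 − p)δ.
- Follow-up only: T + pδ, so the bias is pδ.

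With δ = 0.2 SD (assumed), the bias in the change contrast is −0.2 at p = 0, −0.1 at p = 0.5 and 0 at p = 1. Neither δ nor p can be read from the documents.

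**3. Effect on the test (assumed inputs)**

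Take n independent records per arm, baseline/follow-up correlation 0.5, unit SD and a two-sided 5% test. SE = sqrt(2 × 2(1 − 0.5)/n). Rejection when T = 0 is P(Z > 1.96 − b/SE) + P(Z < −1.96 − b/SE), where b is the size of the remaining bias.

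| n per arm | SE | b = 0.1 SD | b = 0.2 SD |
|---|---|---|---|
| 20 | 0.316 | 6% | 10% |
| 40 | 0.224 | 7% | 15% |
| 80 | 0.158 | 10% | 24% |

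The SAP counts provider records by patient, not by therapist, and this table ignores clustering. It shows scale only.

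**4. Does the SAP's baseline comparison settle it?**

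Power of a baseline test to detect 0.3 SD is approximately Φ(0.3 × sqrt(n/2) − 1.96). For n = 20, 40 and 80 per arm (assumed) this is 0.16, 0.27 and 0.48. With n divided by 1.8, the SAP's largest design effect, it is 0.11, 0.17 and 0.29. A non-significant result does not exclude a shift of that size. Nor can a baseline taken after disclosure separate chance imbalance from a disclosure effect.

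**5. Selective loss (assumed)**

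Suppose the lowest 5%, 10% or 20% of therapists on a normally distributed prognostic trait leave one arm only. The mean of those retained (fraction r) moves by φ(c)/r, where c is the cut-point: 0.11, 0.20 and 0.35 SD.

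**The case against.** Several points on the other side stand.

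- A reader might infer that capacity is an entry condition, so that a therapist who answers no is lost. The documents do not say so. A no at Step 6 leads to troubleshooting, Step 2 lets therapists take as many patients as their schedule allows, and Step 15 raises discontinuation only after six weeks without a referral. The question reads as a retention check.
- A reader might infer that availability is never raised before randomisation. That cannot be shown. The load is stated on the consent call, and the items of the therapist screen are not available.
- A reader might infer that any baseline shift enters the estimate in full, with opposite sign. That holds only if it has vanished by weeks 4, 8 and 12. Therapists know their arm throughout, so some or all of the shift may cancel. If enthusiasm for WILLOW improved baseline scores and then faded, the bias would run against WILLOW.
- The general promotion of WILLOW on the consent call is heard by all therapists before allocation. It is not an arm effect, and reordering the baseline would not remove it.
- The SAP does not list which provider outcomes have a baseline. Its two examples of follow-up-only outcomes, alliance and use of therapy tasks, are untouched by the baseline problem.

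The Step 6 script does hold back further condition detail until the surveys are done. That is only a partial safeguard: the arm has been named, and WILLOW therapists hear about training and payment on the same call.

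**Conclusion.** The point holds as a risk of bias, not as bias shown. The therapist baseline survey follows both randomisation and disclosure of the arm, and so does the first scripted check of availability and caseload room. Provider outcomes tested by Time X Condition may carry a bias equal to the part of the disclosure shift that does not persist to follow-up. Its size and direction cannot be determined from the documents, and the figures in the working rest on assumed inputs. Therapist loss after allocation may also differ by arm, but no loss figures are given.

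The baseline problem is confined to provider outcomes with a baseline, which the documents do not identify. It does not reach follow-up-only outcomes, or patient-reported outcomes that use the patient's own baseline. Both could still be affected by arm-dependent therapist loss. It would go too far to conclude that the trial's results favour WILLOW for this reason.

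**What to change.** **Protocol.** Ask the availability and caseload question on the Step 2 consent call. Send the therapist baseline survey with the Step 3 consent survey. Randomise at Step 5 only when both are complete, and keep the Step 6 call for disclosure and next steps. Reconcile the combined consent and baseline wording in Step 4, item 1 with that order.

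The cost is one question moved and one survey link sent earlier. Some therapists may drop out before randomisation, which is the better side of it. Therapists returning from the pilot keep their earlier arm, so reordering cannot mask them.

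**Data already collected in the current order.** The SAP is written in the past tense, so this is probably the usable part.

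- Report all randomised therapists by arm and by stage of loss: before baseline, before first patient, later.
- Name the provider outcomes that use a therapist baseline, and give their baseline differences with confidence intervals.
- Add a sensitivity analysis of those outcomes by Condition at follow-up, without the post-disclosure baseline. Keep the main analysis, because the follow-up contrast carries any persisting shift and drops adjustment for chance imbalance.

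In the simple two-time-point case, the contrast variances are 4(1 − ρ)/n for change and 2/n for follow-up only. At ρ = 0.5 and n = 40 both are 0.05. Above ρ = 0.5 the sensitivity analysis is the less precise of the two. It does not address therapist loss, which is why the report of loss by arm is also needed.
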